-  The diagnostic LP will be the baseline LP and must be performed in lateral decubitus position. Patients with ICP <25 cm CSF at diagnosis will be excluded
-  Lumbar puncture to be performed after visual assessment. CSF sample from visit 10 LP will be retained for future potential analysis
-  Patients will be provided with training on the self-administration of the trial medication. The patient will be asked to self-administer placebo at visit 1 to demonstrate ability to self-inject. Patients who are not comfortable to self-inject will be excluded
-  If patients discontinue in the randomised double-blind treatment period they will be encouraged to return for all trial visits up to visit 11. If a patient does not want to return for all visits then they will be asked to return at a minimum for visit 11 procedures for safety follow up
-  In the 4 weeks prior to visit 10, patients must not have missed more than one dose of trial medication and must have self-administered their final dose within 7 days of visit 10. Patients will be reminded by the trial site to self-administer trial medication weekly, to continue this until the completion of visit 10 and to bring their trial medication with them at visit 10 for return.  
Where more than one dose has been missed during the preceding 4 weeks, visit 10 should be delayed. Self-administration of trial medication should continue at 7-day intervals and then visit 10 rescheduled to ensure no more than one dose of the trial medication has been missed in the previous 4 weeks. Visit 10 should be delayed no more than 14 days
-  Optional unscheduled visit for visual testing (HVF, OCT, LogMAR) for patients in whom there is concern about visual decline or who perform inadequately or where there is technical failure (more than 15% false positive responses or inadequate performance indicated by the Visual Field Reading Centre for HVF; or OCT imaging not of satisfactory quality as determined by the OCT Reading Centre)
-  In the event of any abnormal safety assessments identified at end of treatment, e.g., abnormal ECG, abnormal routine laboratory results or ongoing adverse events, this visit may be performed at the clinic to repeat or follow up safety assessments
-  Reporting of AEs/SAEs will continue up to the final follow up visit 11

Study Number: INVEX-CLIN-IIH-301 Protocol	Compound No.: Presendin

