- Trial medication dispensed and first dose self-administered at clinic. Patients will then be instructed to administer subsequent doses once weekly.
- Pharmacokinetic sampling (post-dose)

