In the 4 weeks prior to visit 10, patients must not have missed more than one dose of trial medication and must have self-administered their final dose within 7 days of visit 10. Patients will be reminded by the trial site to self-administer trial medication weekly, to continue this until the completion of visit 10 and to bring their trial medication with them at visit 10 for return.

Where more than one dose has been missed during the 4 weeks preceding visit 10, visit 10 should be delayed. Self-administration of trial medication should continue at 7-day intervals and then visit 10 rescheduled to ensure no more than one dose of the trial medication has been missed in the previous 4 weeks. Visit 10 should be delayed no more than 14 days.

- Concomitant medication review
- Headache preventative medication review
- Headache diary review

Study Number: INVEX-CLIN-IIH-301 Protocol	Compound No.: Presendin
	Version: 3.0

- Vital signs (triplicate readings for blood pressure and heart rate will be taken at 1-minute intervals)
- Body weight and BMI
- Adverse event review
- Targeted physical examination
- Urine pregnancy test for women of child-bearing potential
- Electrocardiogram
- Visual Assessments to both eyes
  - Optical coherence tomography Imaging
    - Sites should initially check the scan quality. The OCT scan should then go through the upload process to the OCT Reading Centre, without delay. The OCT scan will then be reviewed by the OCT Reading Centre for a full quality assessment. The report from the OCT Reading Centre will be sent to the site. Where the OCT is of insufficient quality it should be repeated as soon as possible at an unscheduled visit. Where the OCT processing is of insufficient quality it should be reprocessed as soon as possible by the site.
  - Humphrey Visual Field (24-2 SITA-Standard)
    - Sites should initially check the performance quality of the HVF (to ensure no more than 15% false positives). The HVF should then be uploaded to the Visual Field Reading Centre without delay (an initial quality assessment takes place during the upload procedure). The HVF will then be reviewed by the Visual Field Reading Centre for a full quality assessment. The report from the Visual Field Reading Centre will be received by the site. Where the visual field is of insufficient quality it should be repeated at an unscheduled visit without delay.
  - Visual Acuity (LogMAR score)
- Lumbar puncture (within 7 days of last dose of trial medication)

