  - Lumbar puncture to be performed ideally after visual assessments
  - Performed in the lateral decubitus position according to LP SOP
  - In some cases the lumbar puncture might be conducted using imaging guidance according to the preference of the individual and site. This could be using x-rays, computer tomography or ultrasound guidance.

Study Number: INVEX-CLIN-IIH-301	Compound No.: Presendin
Protocol	Version: 3.0

- If the procedure is not successfully performed it should be re-booked and repeated as soon as possible and the patient should remain on trial medication with the last dose within 7 days of the LP.
- Patient reported outcomes: VFQ-25 & 10-item supp, HIT-6, SF-36 and EQ-5D-5L in diary
- Health Utilisation Form
- Patient global impression of change question
- Laboratory assessments
- Pharmacokinetic blood sampling
- Anti-drug antibodies blood sampling
- Trial medication accountability

Where it is not feasible to conduct all of visit 10 procedures on the same day, these could be split provided visual assessments are performed before the LP and the patient remains on trial medication with the last dose within 7 days of the LP.

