### **6.3. Efficacy Procedures**

#### **6.3.1. Intracranial Pressure**

Assessment of ICP will be measured by LP in the lateral decubitus position. The diagnostic LP is performed by the clinical team prior to recruitment and the measurement must be made from the lateral decubitus position. The research LP will be performed according to LP standard operating procedure (SOP). Lumbar puncture will ideally be performed after visual assessments as outlined in the Time and Events table ([Table 1](#)).

In some cases the lumbar puncture might be conducted using imaging guidance according to the preference of the individual and site. This could be using x-rays, computer tomography or ultrasound guidance.

Any additional LP procedures, outside of the protocol would constitute a protocol deviation and ideally should be discussed with the Investigator before the procedure is performed.

Non-protocol LPs should be recorded in the Case Report Form.

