To minimize direct, in-person contact between site personnel and patients, certain procedures may be performed remotely via telemedicine. All other procedures should be done in-person while the subject is on-site. Specifically, the following procedures may be done remotely:

- Concomitant medication review
- Headache preventative medication review
- Headache diary review
- Adverse events
- Patient reported outcomes
- Health utilisation form

- **Visit 10**

There are essential aspects to these visits which must be performed in person. Where this is not possible due to the pandemic or other global crisis the following components of the visit should be performed at the next available opportunity in line with the schedule of assessments table:

- Vital signs
- Body weight and BMI
- Physical examination
- Urine pregnancy test
- Electrocardiogram
- Optical coherence tomography imaging
- Humphrey Visual Field
- Visual acuity testing
- Laboratory assessments
- Pharmacokinetic sampling
- Anti-drug antibodies sampling

Study Number: INVEX-CLIN-IIH-301 Protocol	Compound No.: Presendin
	Version: 3.0

- Lumbar puncture\*

\* Lumbar puncture to be ideally performed after visual assessments. In the 4 weeks prior to visit 10, patients must not have missed more than one dose of trial medication and must have self-administered their final dose within 7 days of visit 10. Patients will be reminded by the trial site to self-administer trial medication weekly, to continue this until the completion of visit 10 and to bring their trial medication with them at visit 10 for return.

Where more than one dose has been missed during the preceding 4 weeks, visit 10 should be delayed. Self-administration of trial medication should continue at 7-day intervals and then visit 10 rescheduled to ensure no more than one dose of the trial medication has been missed in the previous 4 weeks. Visit 10 should be delayed no more than 14 days, if possible, but this can be extended according to local government policy if a patient is unable to attend (for example if a patient is self-isolating) as long as medication use is maintained as above.

- Follow up/ Visit 11

This should be performed as a telephone visit unless clinical contact is necessary, as per protocol. Where face to face contact is required, this should be conducted at the earliest available opportunity.

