#### **13.3.1.2.2. Intercurrent event: Off-protocol lumbar punctures**

As discussed above, LPs are a material and widespread intervention in the treatment of IIH, given with the intention of reducing intracranial pressure and improving the associated symptoms of the disease, including reducing pressure on the optic nerve and papilloedema, allowing visual fields to improve. Patients that have LPs are expected to experience less pressure on the optic nerve, less papilloedema, and have better chances of

Study Number: INVEX-CLIN-IIH-301 Protocol	Compound No.: Presendin
	Version: 3.0

their visual fields improving. Beneficial effects dissipate with time and whilst there has been no longitudinal assessment to quantify papilloedema after an LP the consensus of clinicians would predict that effects of the LP on papilloedema and therefore visual fields would have dissipated by one month. Outcomes from patients that have undergone off-protocol LPs will confound the estimation of the causal treatment effect of Presendin. PMD outcomes will be recorded repeatedly during the trial. For the reasons stated, we propose to remove PMD outcomes recorded in the 4-weeks following an off-protocol LP, and replace these observations with patient-within-arm imputations generated by a method suitable for longitudinal data imputation.

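### Visit 10: protocol v3.0 contradicts itself on whether visual tests must precede the lumbar puncture, and its 4-week removal rule does not reach visual repeats made after the scheduled puncture

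*Protocol*

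**What the plan says.** All references are to protocol v3.0.

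**Order at Visit 10.** Three operative passages make the order a preference:
- 6.1.5 (Visit 10): "Lumbar puncture to be performed ideally after visual assessments"
- 6.3.1 (Intracranial Pressure): "Lumbar puncture will ideally be performed after visual assessments"
- Section 7 (global crisis, Visit 10): "Lumbar puncture to be ideally performed after visual assessments"

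Two passages make it a requirement:
- Table 1, footnote 9: "Lumbar puncture to be performed after visual assessment"
- 6.1.5, on spreading Visit 10 over several days: "these could be split provided visual assessments are performed before the LP"

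**Repeats for quality.** At Visit 10 the site checks each field and OCT and uploads them, and the Reading Centres then make the full quality assessment. For a rejected field, "Where the visual field is of insufficient quality it should be repeated at an unscheduled visit without delay". A rejected OCT is likewise repeated at an unscheduled visit. No passage makes the LP wait for the Reading Centre report.

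**What the plan says an LP does.** Section 1.1 says an LP can change measurements of papilloedema in some patients. Sections 13.3.1.2.2 and 13.3.1.3.2 expect the effect on papilloedema, and hence on fields, to be gone by one month.

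**Removal rule.** Section 13.3.1.2.2 states: "we propose to remove PMD outcomes recorded in the 4-weeks following an off-protocol LP". Section 13.3.1.3.2 has the same rule for OCT. Section 6.3.1 treats LPs outside the protocol as deviations; the scheduled Visit 10 LP is not one of them.

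**Estimand.** Section 13.3.1.5 defines the PMD effect over 24 weeks as if patients had no procedures likely to affect PMD materially.

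**The concern.** There are two linked defects. First, a site that performs the LP before the fields and OCT on the same day is consistent with 6.1.5, 6.3.1 and Section 7 but in breach of footnote 9. Measurement order is site conduct, so no analysis document can restore it afterwards.

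Second, obeying footnote 9 does not close the gap. If the LP is done on the visit day and the Reading Centre later rejects the field or OCT, the repeat comes after the LP. The plan would discard the same measurement if the preceding LP had been unscheduled, yet its written rule does not mention the LP that every patient is scheduled to have.

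PMD is the initial secondary endpoint and one of the two outcomes on which the trial was sized, and OCT is the papilloedema endpoint. What is at stake is the Week-24 value of both: some could reflect CSF removal rather than treatment, contrary to the stated PMD estimand.

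**Working it through.** **1. Order, passages side by side.**

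| Place | Visual tests before LP? |
|---|---|
| 6.1.5, LP bullet | preferred |
| 6.3.1 | preferred |
| Section 7, Visit 10 | preferred |
| Table 1, footnote 9 | required |
| 6.1.5, split-visit proviso | required |

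These cannot all govern the same visit.

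**2. Does a test after the LP fall in the plan's own 4-week period?** Table 1 sets Visit 10 at Day 169 ± 14, that is Days 155 to 183. Two procedures inside that window are at most 183 − 155 = 28 days apart, exactly four weeks. So any field or OCT taken after the LP within the Visit 10 window is inside the period that the rule treats as affected. With the LP on Day 169, the period runs to Day 169 + 28 = 197, so a prompt repeat falls well inside it.

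**3. Does the rule reach it?** The rule requires an off-protocol LP. The Visit 10 LP is on-protocol. As written, it does not.

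**4. The plan's PMD figure.** Section 13.2.1.1 (PMD power) gives 142 patients in total for 0.71 dB, SD 1.8, 90% power, correlation 0.4, with measurements at 0, 0.5, 1, 2, 3, 4, 5 and 6 months. The slope formula per arm is

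m = 2(z_α + z_β)² SD² (1 − ρ) / (Sxx d²).

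Here the mean time is 2.6875, Sxx = 91.25 − 8 × 2.6875² = 33.47, and d = 0.71/6 per month. At a one-sided 5% level m = 71.05, so the total is 142. At ρ = 0.3, m = 82.89, total 166. A two-sided 5% level gives 176 and 204; that is a separate matter. The present point disputes none of these figures. The formula serves only to show how much weight Week 24 carries.

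**5. Size, under assumptions that are not in the documents.** Suppose a share f of one arm has its Week-24 PMD shifted by s dB and the other arm has no shift.
- Week-24 contrast moves by f × s.
- Slope analysis: multiply by 6 × (6 − 2.6875)/33.47 = 0.594.
- Average of the seven post-baseline visits: divide by 7.

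| f | s (dB) | Week 24 (dB) | Slope (dB) | Average (dB) |
|---|---|---|---|---|
| 0.10 | 0.25 | 0.025 | 0.015 | 0.004 |
| 0.25 | 0.50 | 0.125 | 0.074 | 0.018 |
| 0.50 | 1.00 | 0.50 | 0.297 | 0.071 |

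At Week 24 these are 3.5%, 17.6% and 70.4% of 0.71 dB. The last row needs half of one arm, and nobody in the other, to be affected. If the affected share and the shift are the same in both arms, the contrast does not move.

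**The case against.** The strongest reply is that this is loose wording and nothing more. Footnote 9 is unconditional, the split-visit proviso agrees with it, 6.1.5 lists the visual tests before the LP, and section 1.1 explains why that order is wanted. No passage directs an LP-first visit. This stands: a reader might infer that the protocol permits the LP first, but the documents show a contradiction, not a permission.

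Nor do all repeats follow the LP. The site checks quality first, fields are also assessed during upload, and some OCT failures need only reprocessing. The LP may also be on a later day or re-booked. This stands too: the route exists only where the LP is done before the report arrives.

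A reader might also infer that values after the LP are kept in the analysis. The written rule does not remove them, but no passage says that an unscheduled repeat becomes the Week-24 record. Record selection is properly left to the SAP, which is not shown. What remains is that the protocol itself fixes the scope of the removal rule, and that scope omits the scheduled LP.

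It is tempting to extend the point to Visit 2, where the text reads "Trial medication dispensed and first dose self-administered at clinic" and rejected tests are also repeated at an unscheduled visit. No passage says that a post-dose repeat serves as baseline, and Visit 1 values that go through Reading Centre review exist, so this is not supported. Nor is an extension to visual acuity: the one-month statements concern papilloedema and fields.

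**Conclusion.** The point holds as a contradiction to be reconciled and a rule drawn too narrowly. Both can be shown from the v3.0 text alone, and both merit correction because the order of measurement cannot be repaired after the visit.

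The direction and size of any bias cannot be derived from the documents. A reader might take the drop in pressure quoted in 13.3.1.1.2 (32 to 19 cm CSF) as a measure of the harm, or assume that an LP erases the arm difference in affected patients. Neither is supported: that drop is opening pressure against pressure just after an LP, not a PMD or between-arm effect, and a shift common to both arms cancels. With the PMD effect defined over 24 weeks and eight measurement occasions planned, the consequence is probably small unless many patients are affected and mostly in one arm. No sample size or power figure changes.

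The conclusion assumes that the v3.0 text is still in force. Of v4.0 only appendix pages are available, so its Visit 10, LP and estimand sections must be checked.

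**What to change.** 1. Reconcile 6.1.5, 6.3.1 and Section 7 with Table 1 footnote 9, so that all state that visual assessments precede the Visit 10 LP.
2. In 13.3.1.2.2 and 13.3.1.3.2, extend the 4-week rule to the scheduled Visit 10 LP: PMD and OCT values recorded in the four weeks after it are set to missing in the efficacy analyses and imputed as already planned. Repeats for safety continue and are reported.
3. Confirm whether the v4.0 body still carries the present wording, and amend that version if so.

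The second step covers repeats after rejection without asking sites to hold the LP for the report. The cost is wording, plus a few Week-24 values lost. Patients concerned still have up to six earlier post-baseline occasions for the longitudinal imputation to use, and the PMD sample size already allows for 30% loss (166/0.7 = 237, against 240 planned).

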#### **6.1.6. Visit 11 Follow-Up**

This visit will be performed as a telephone call to conduct headache preventative medication review and check for any AEs or changes in medication. In the event of any abnormal safety assessments identified at the end of treatment, e.g., abnormal ECG, abnormal routine laboratory results or ongoing adverse events, this visit may be performed at the clinic to repeat or follow up safety assessments.

A urine pregnancy test (for women of childbearing potential) will be performed, this can be conducted at home if the visit is performed by telephone call.

#### **6.1.7. Unscheduled visit for repeat visual assessments**

Optional unscheduled visit for visual testing (HVF, OCT, LogMAR) for patients where there is concern about their visual decline or who perform inadequately or where there is technical failure (more than 15% false positive responses or inadequate performance indicated by the Visual Field Reading Centre for HVF; or OCT imaging not of satisfactory quality as determined by the OCT Reading Centre). Imaging only in the study eye(s).

- Optical coherence tomography Imaging

Study Number: INVEX-CLIN-IIH-301 Protocol	Compound No.: Presendin
	Version: 3.0

- Sites should initially check the scan quality. The OCT scan should go through the upload process to the OCT Reading Centre. The OCT scan will then be reviewed by the OCT Reading Centre for a full quality assessment. The report from the OCT Reading Centre will be sent to the site. Where the OCT is of insufficient quality it should be repeated as soon as possible at an unscheduled visit. Where the OCT processing is of insufficient quality it should be reprocessed as soon as possible by the site.
- Humphrey Visual Field (24-2 SITA-Standard)
  - Sites should initially check the performance quality of the HVF (to ensure no more than 15% false positives). The HVF should then be uploaded to the Visual Field Reading Centre without delay (an initial quality assessment takes place during the upload procedure). The HVF will then be reviewed by the Visual Field Reading Centre for a full quality assessment. Quality reports from the Visual Field Reading Centre will be received by the site. Where the visual field is of insufficient quality it should be repeated at an unscheduled visit without delay.
- Visual Acuity (LogMAR score)

## 6.2. Trial Procedures

### 6.2.1. Screening Procedures

#### 6.2.1.1. Demographics

The Investigator, or designee, should record the patient's sex, ethnicity, age, height, body weight and BMI at screening.

Ethnicity data will be collected in order to monitor any response differences in IIIH disease progression/symptoms in different ethnicities.

#### 6.2.1.2. Medical, Headache and Ophthalmic History

The Investigator, or designee, should record any ongoing co-morbidities and significant medical, headache and ophthalmic history along with the year in which such co-morbidities began (where known).

#### 6.2.1.3. Reporting of Prior and Concomitant Medication

Concomitant treatment is any medication or therapeutic intervention being continued by the patient at trial entry and any new medication received during the trial. Prior treatment

Study Number: INVEX-CLIN-IIH-301 Protocol	Compound No.: Presendin
	Version: 3.0

includes previous medications, treatments and interventions received in the past but no longer ongoing.

For this trial, only relevant prior concomitant medications within the last 4 months will be recorded. These include:

- Treatment to lower ICP (e.g., acetazolamide, topiramate (including if used as a migraine preventative), diuretics, glucocorticoids (I.V., injectable steroids or oral (including dexamethasone and prednisolone)). (Nasal, inhaled, or topical steroids are allowed)
- Headache preventative medication (including oral or botulism toxin A or monoclonal antibodies against CGRP or CGRP antagonists, or greater occipital nerve block)
- GLP-1 receptor agonist
- Warfarin
- Glucose lowering medication
- Recreational or illicit drugs

At every visit the Investigator or a qualified designee will ask the patient about relevant concomitant medication.

No new medication should be started during the trial, unless medically necessary. The patient should be advised to consult the Investigator or designee before taking any prescribed or over-the-counter medications. In the case of headache preventative medications or ICP lowering medications please see details in the rescue therapy section. Acute headache analgesics are permitted and should be reported in the diary.

